**1. INTRODUCTION**

Glaucoma is a group of eye diseases characterized by progressive, irreversible and largely asymptomatic vision loss caused by optic nerve damage, which is most commonly associated with elevated levels of intraocular pressure. Glaucoma is a chronic condition that progresses slowly over long periods of time and can have a devastating impact on a patient's vision and quality of life. Reducing intraocular pressure is the only proven treatment for glaucoma.

Treatment for open-angle glaucoma (OAG) has started traditionally with topical ocular hypotensive medical therapy. Development of more effective medications has increased the popularity of this approaches as initial treatment compared to more invasive incisional or drainage device surgery. Furthermore, the more benign medication treatments preserve the ocular tissues in the event that more invasive surgical approaches are eventually required.

The various topical ocular medications available to reduce IOP include miotics,  $\beta$ -adrenergic receptor antagonists ( $\beta$ -blockers), carbonic anhydrase inhibitors (CAIs),  $\alpha$ -adrenergic receptor agonists ( $\alpha$ -agonists), and prostaglandin analogues (PGs). The PGs are a class of ocular hypotensive agents that have been proven effective in lowering IOP in subjects with OAG or OHT. Advantages of this class of medications over other classes is that the systemic side effects associated with  $\alpha$ -agonists (e.g., dry mouth, drowsiness) and  $\beta$ -blockers (e.g., depression, fatigue, bradycardia) do not appear to be associated with PGs. Furthermore, the ocular side effects typically associated with  $\alpha$ -agonists (e.g., allergic reactions), and cholinergic agents (e.g., reduced vision), do not seem to manifest with the use of PGs.

In spite of these apparent advantages, PGs have been shown to be associated with side effects such as ocular hyperemia, iris hyperchromia, periorbital atrophy, increased eyelash growth, general ocular surface discomfort and headache. These side effects and other factors including cost, compliance, and the difficulty of proper instillation, hinder the proper use of topical medications. Some patients may possess or develop an intolerance to topical medications.

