**9.6.5. Safety Analyses**  
No formal statistical testing will be conducted for the safety analyses. No imputation will be performed for the missing values. All summaries will be based on the available data of the safety population. The descriptive statistics described in Section 9.6.1 will be performed at each visit for the 3 treatment groups separately. Sections below described specific data handling for study drug exposure, surgical complications, adverse events, and best spectacle corrected visual acuity (BCVA).

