### 7.1.2. Adverse Events

All adverse event (AE) summaries will be restricted to Treatment Emergent Adverse Events (TEAE), which are defined as those AEs that occurred on/after the initial treatment at Visit 3. Verbatim terms reported by the study sites will be mapped to system organ classes (SOC) and preferred terms assigned using MedDRA (Medical Dictionary for Regulatory Activities) [REDACTED] for summary purposes. The adverse event listings will be displayed by treatment group. The number and of percentage subjects experiencing a particular event will be presented.

For a given AE and subject, if more than 1 severity grade is reported, the highest severity grade will be used for analysis.

If a subject experienced more than 1 relationship within an AE, the subject is counted once under maximum relationship. AEs with a missing relationship will be considered related for this summary; events classified as ‘possibly’, ‘probably’ or ‘definitely’ from eCRF will be considered ‘related’.

Adverse events will be classified into ocular AEs and non-ocular/non-study eye AEs. An ocular AE will be determined as indicated on the AE form of eCRF for the study eye only; a non-ocular/non-study eye AEs will include AEs with primary SOCs of eyes for non-study eye and AEs with primary SOCs not for eye.

All TEAEs, ocular TEAEs and non-ocular/non-study eye TEAEs will be summarized by treatment group separately in the following tables:

- Summary of adverse events
- TEAE by SOC and preferred term
- TEAE by SOC, preferred term and maximum severity.
- TEAE by SOC, preferred term and relationship (Related/Not Related) to study treatment.
- Serious TEAEs by SOC and preferred term.
- Ocular TEAEs by preferred term.

The TEAE listings will be prepared, sorted chronologically within subjects for the following types of AEs. Each listing will be displayed by treatment group.

- All AEs
- Serious AEs
- TEAEs leading to death
- TEAEs leading to withdrawal [REDACTED]

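### SAP 7.1.2 counts fellow-eye and systemic adverse events in one class, so no subject-level systemic total by arm is specified

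*SAP*

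**What the plan says.** SAP 7.1.2 (Adverse Events) sets up two reporting classes: "Adverse events will be classified into ocular AEs and non-ocular/non-study eye AEs". The first is limited to one eye: "An ocular AE will be determined as indicated on the AE form of eCRF for the study eye only". The second takes the rest: "a non-ocular/non-study eye AEs will include AEs with primary SOCs of eyes for non-study eye and AEs with primary SOCs not for eye". No class, and no stated total, covers events in neither eye.

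The same section says how the classes are shown: "All TEAEs, ocular TEAEs and non-ocular/non-study eye TEAEs will be summarized by treatment group separately in the following tables". The list starts with an overall summary whose rows are not described. It continues with "TEAE by SOC and preferred term", then versions by maximum severity, by relationship and for serious events. For each event, "The number and of percentage subjects experiencing a particular event will be presented". Listings of AEs by arm are also planned. SAP Section 1 places the table shells in a separate document.

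Two protocol statements bear on the point. Section 1 contrasts prostaglandins with beta-blockers and, from inside a bracket of systemic examples, reads "e.g., depression, fatigue, bradycardia) do not appear to be associated with PGs". Section 9.6.5 states: "No formal statistical testing will be conducted for the safety analyses".

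**The concern.** The safety objective compares the implants with timolol, and control subjects instil timolol twice daily for three years. The protocol's own background names systemic effects as a difference between the two drug classes. The share of subjects in each arm with any systemic TEAE, and with a serious or related one, is therefore a natural line in the safety summary.

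Under the two-class rule the nearest specified figure is the total for the pooled class. That total also counts subjects whose only event was in the fellow eye. Such events say little about systemic tolerability. If they are about equally common in every arm, they draw the arm totals together. With no safety test planned, the displayed totals carry more of a reader's judgement.

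**Working it through.** The plan states no adverse event rate, so there is no figure to reproduce. The check has three steps.

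**1. Where each kind of event lands (SAP 7.1.2)**

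| Location of event | Coded to the eye SOC | Coded to another SOC |
|---|---|---|
| Study eye | Ocular class | Ocular class by the AE form, but it also fits the wording of the second class |
| Fellow eye | Pooled class, eye-SOC row | Pooled class, non-eye row |
| Neither eye | (not expected) | Pooled class, non-eye row |

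Fellow-eye events coded to the eye SOC stay out of the non-eye rows, so they do not dilute the systemic SOC and preferred-term rows. They also supply the eye-SOC row of the pooled class, which is why that row largely shows the fellow-eye rate. The exception is a fellow-eye event coded to a non-eye SOC, which falls in rows that will be read as systemic.

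**2. Whether a systemic total can be recovered from the tables**

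A subject with events in two SOCs appears in two SOC rows but once in a total, so rows cannot be added. Let T be the class total, F the eye-SOC row and S the number with any systemic event. Assume all fellow-eye events are coded to the eye SOC. Then T − F ≤ S ≤ T. The largest non-eye row can raise the lower limit, and the sum of the non-eye rows can reduce the upper one. The tables therefore give limits, not the count.

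**3. Size of the dilution in a class total**

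Inputs, all assumed: systemic rate s = 20% on an implant and 30% on timolol; fellow-eye rate f equal in both arms and independent of systemic events.

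Pooled rate = 1 − (1 − s)(1 − f)

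Pooled difference = (s_timolol − s_implant)(1 − f)

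| f | Implant | Timolol | Difference (points) | Ratio |
|---|---|---|---|---|
| 0% | 20.0% | 30.0% | 10.0 | 1.50 |
| 5% | 24.0% | 33.5% | 9.5 | 1.40 |
| 10% | 28.0% | 37.0% | 9.0 | 1.32 |
| 25% | 40.0% | 47.5% | 7.5 | 1.19 |
| 40% | 52.0% | 58.0% | 6.0 | 1.12 |

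Worked line for f = 10%: 1 − 0.80 × 0.90 = 0.28; 1 − 0.70 × 0.90 = 0.37; difference 0.09 = 0.10 × 0.90.

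Applying step 2 to that line, S lies between 28 − 10 = 18% and 28% on the implant, and between 37 − 10 = 27% and 37% on timolol, before any tightening from the SOC rows.

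For scale, about 150 subjects randomized 1:1:1 is 150 / 3 = 50 per arm. Ten points is then 5 subjects, 9 points is 4.5 and 7.5 points is 3.75. The loss is about half a subject at f = 10% and 1.25 subjects at f = 25%.

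**The case against.** The best reply is that the tables that matter most are already planned. Depression, fatigue and bradycardia are specific terms. Each would have its own preferred-term row by arm, with severity, relationship and seriousness breakdowns, and fellow-eye events in the eye SOC do not touch those rows. Neither document makes a composite of all systemic events an objective or endpoint. No safety test exists to lose power. The shells, which are not available here, may already carry a systemic subtotal, and a subject-level count could be derived from the listings.

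Most of this stands, and it rules out two stronger readings.

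- A reader might infer that no systemic adverse event rate will be reported. That is wrong: SAP 7.1.2 tabulates the pooled class by SOC and preferred term for each arm.
- A reader might infer that the fellow-eye rate is lost as a reference for the study eye. That is mostly wrong, because the eye-SOC row of the pooled class largely shows it.

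The assumption of equal fellow-eye rates also cannot be checked, since part of the dosing text is redacted. If the rates differed between arms, the pooled difference could move either way.

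The reply does not supply the missing total. The SAP text requires none, and the overall summary it lists is not broken down by SOC. Working a count out of listings is a task for the plan, not for the reader of the report.

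**Conclusion.** The point holds as a minor one. SAP 7.1.2 specifies no subject-level systemic total, whether for any, serious or related events or by maximum severity. Totals for the class that contains systemic events mix in fellow-eye events. The effect is confined to aggregate rows; systemic SOC and preferred-term rates are unaffected, apart from fellow-eye events coded outside the eye SOC.

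In those totals a true difference shrinks by the factor 1 − f, for example from 10 points to 9 at f = 10% or 7.5 at f = 25%. This rests on assumed systemic rates and on a fellow-eye rate that is equal across arms and independent of systemic events. None of these comes from the documents, so the actual size is unknown. Because the safety analysis is descriptive, no planned inference is affected.

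**What to change.** In SAP 7.1.2, replace the two classes with three defined by location: study eye, fellow eye, and systemic (neither eye). Assign the class from the recorded eye first, and use SOC only to arrange rows within a class. Produce the listed tables for systemic TEAEs on their own, plus a short SOC and preferred-term table for the fellow eye. This would also settle where a study-eye event coded to a non-eye SOC belongs.

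At minimum, keep the present classes and add systemic-only total rows, by arm, to the summary, maximum-severity, relationship and serious-event tables.

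The cost is SAP wording before the Month 36 lock and a small amount of standard output. One check is needed. The present rule already relies on laterality for eye-SOC events, but the AE form contents listed in protocol Section 10 do not mention the affected eye. Confirm that laterality is recorded for events coded to non-eye SOCs; where it is not, review those terms before lock and document the assignment.

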#### 7.1.3. Best Spectacle Corrected Visual Acuity (BSCVA)

BSCVA will be measured for both eyes using the logMAR chart at all scheduled visits except on the surgery day, Day 1-2, and Day 10. Number of letters correct at 4 meters will be collected.

The number and percentage of subjects in each category will be presented. Similar analyses on change in number of letters correct from baseline will be conducted by visit.

In addition, the actual value and change from baseline in number of letters correct will be calculated for each post-baseline visit and summarized as continuous variable by treatment group.

[figure not shown]
#### 7.1.4. Slit Lamp Examination and Implant Assessment

The slit lamp examination will include the measurement of aqueous cell and flare by a standard grading system and an evaluation for the presence of corneal abnormalities, pupillary irregularities, iris atrophy and pigment dispersion. Crystalline lens status (for phakic subjects) will also be assessed. Slit lamp examination will be performed for the study eye at each scheduled visit except the surgery day. Severity grades for the findings are:

For the evaluation of aqueous cells and flare, the following grading schemes are used:

- [REDACTED]
- [REDACTED]
- [REDACTED]
- [REDACTED]

The frequency distribution for the severity grade at each scheduled visit will be summarized by treatment group for the study eye.

[REDACTED]

[REDACTED]

[REDACTED]

Slit lamp examination and implant assessment will be presented in data listings.

#### 7.1.5. Gonioscopy

Gonioscopy will be used to assess angle abnormalities including presence of goniosynechiae, angle anatomy and implant location (in subjects with implants). At the screening exam, the following data will be collected:

[REDACTED]

[REDACTED]

[REDACTED]

The number and percentage of subjects in each category will be summarized.

Gonioscopy findings include abnormal anatomy, goniosynechiae, rubeosis, and other angle abnormalities. The number and percentage of subjects with the gonioscopy findings at each scheduled visit will be summarized by treatment group for the study eye.

[REDACTED]

[REDACTED]

### 7.1.6. Ophthalmoscopy

Ophthalmoscopy will be performed with pupil dilation to examine the fundus and nerve abnormalities for the study eye at Screening, Weeks 4, 6, Months 3, 6, 9, 12, 15, 18, 21, 24, 27, 30, 33, and 36. The dilated fundus exam will include evaluation of the macula and vessels as well as peripheral fundus examination.

In addition, the number and percentage of subjects with any clinically significant findings at any post-baseline visits, and at each scheduled post-baseline visit will be also presented by treatment group.

### 7.1.7. Visual Field

Visual fields will be obtained with standard, white-on-white, automated threshold perimetry using Humphrey 24-2, SITA Standard, or Octopus 24-2 Dynamic, or equivalent at Screening, Months 6, 12, 18, 24, 30, and 36.

The same test methodology must be used throughout the entire study for a given subject. Visual field mean deviation (MD) and pattern standard deviation (PSD) will be recorded in decibels (dB). The actual value and change from baseline in MD, and pattern standard deviation will be calculated for each post-baseline visit and summarized as continuous variable by treatment group.

### 7.1.8. Vertical Cup-to-Disc Ratio

The cup-to-disc (C/D) ratio is a numerical expression indicating the percentage of disc occupied by the optic cup. Vertical C/D ratio will be assessed, and a score from 0.1 to 0.9 (in 0.1 increments) will be recorded for the study eye at Screening, and Months 6, 12, 18, 24, 30, and 36. The change from baseline in C/D ratio at each follow-up visit will be categorized as:

The actual value and change from baseline in vertical C/D ratio for the study eye will be calculated for each post-baseline visit and summarized as continuous variable by treatment group.

The number and percentage of subjects in each category listed above will be provided by treatment group for the study eye as overall (i.e., based on the maximum change from baseline across any post-baseline visits), and by visit.

#### **7.1.9. Pachymetry**

[figure not shown]
Pachymetry is performed to determine corneal thickness for the study eye at Screening, and Months 12, 24, and 36. For each evaluation, three measurements are to be taken utilizing an ultrasonic pachymeter and the mean recorded for analysis. The actual value and change from baseline in corneal thickness will be calculated for each post-baseline visit and summarized by treatment group.

#### **7.1.10. Specular Microscopy**

Specular microscopy will be performed in all subjects. Specular microscopic images will be taken in three locations using the microscopes' internal fixation targets (temporal, central, and nasal) of study eyes at Screening, Month 3, Months 12, 24 and 36. Endothelial cell density, percent hexagonality, and the coefficient of variation (COV) will be assessed from calibrated specular microscope images. At each examination, average endothelial cell density for each eye will be reported by the reading center and used for analysis.

[figure not shown]
The actual, change from baseline, and percent change from baseline in central endothelial cell density will be calculated for each post-baseline visit and summarized by treatment group.

In addition, the number and percentage of subjects with the following categories of changes from baseline in central endothelial cell density will be summarized by treatment group for study eye as overall (i.e., based on the minimum change from baseline across any post-baseline visits), and by visit:

[figure not shown]

#### **7.1.11. Conjunctival Hyperemia Assessment**

Conjunctival hyperemia assessment will be performed at Baseline and all scheduled visits from Week 4. Conjunctival hyperemia will be scored [REDACTED]:

[figure not shown]
The number and percentage of subjects in each severity grade will be summarized by treatment group and visit for the study eye, using CRF data and Central Reading Center data separately.

A subject listing will be provided.

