**Safety Variables**

Surgical complications and adverse events will be summarized.

Ocular safety variables, i.e. best spectacle-corrected visual acuity, biomicroscopy findings, gonioscopy findings, ophthalmoscopy findings (including cup/disc ratio), pachymetry, visual field test evaluation and endothelial cell parameters, will be summarized. In addition, changes from baseline in conjunctival hyperemia, periorbital measurements, iris (color) and eyelashes (density and length) will be analyzed, if feasible.

Blood plasma testing will be performed to assess systemic exposure to the implant study medication (travoprost free acid).

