**CLINICAL PROTOCOL**

Date: September 16, 2016	Phase: Phase II Study	Protocol No.: GC-009
-----------------------------	--------------------------	-------------------------

Changes from baseline in conjunctival hyperemia, periorbital measurements, iris color and eyelash density and length will be analyzed, if feasible.

Blood plasma testing will be performed to assess systemic exposure to the implant study medication (travoprost free acid).

Note: See Appendix A for a schedule of visits and assessments, and Appendix I for a detailed description of the study procedures.

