**9.5.2. Safety Outcomes**

The safety outcomes include surgical complications, adverse events, BCVA, slit-lamp biomicroscopy findings, change in gonioscopy findings, ophthalmoscopy findings (including cup/disc ratio), pachymetry, visual field evaluation, endothelial cell parameters, change from baseline in conjunctival hyperemia, periorbital measurements, iris color and eyelash density and length, and blood plasma testing to assess systemic exposure to the implant study medication (travoprost free acid).

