#### 4.1.2. Change and Percent Change from Baseline

- Change from baseline is defined as the post baseline value minus the baseline value.
- Percent change from baseline is calculated as follows: Percent change = (Change from baseline / Baseline) \* 100.

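### SAP 7.1.11 counts hyperemia grades at each visit but names no change-from-baseline summary, so its table cannot show how many subjects worsened

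*SAP*

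**What the plan says.** **Protocol.** Section 9.5.2 includes among the safety outcomes "change from baseline in conjunctival hyperemia, periorbital measurements, iris color and eyelash density and length". Section 5.2 states the plan with a condition attached: "Changes from baseline in conjunctival hyperemia, periorbital measurements, iris color and eyelash density and length will be analyzed, if feasible". The Summary, under Safety Variables, carries the same condition. Section 9.6.5 plans no formal safety tests and gives the general rule: "The descriptive statistics described in Section 9.6.1 will be performed at each visit for the 3 treatment groups separately".

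**SAP.** Section 7.1.11 sets the assessment times: "Conjunctival hyperemia assessment will be performed at Baseline and all scheduled visits from Week 4". Its analysis sentence is "The number and percentage of subjects in each severity grade will be summarized by treatment group and visit for the study eye", done separately on CRF and Central Reading Center data, followed by a subject listing. The visible text names no change, shift or worsening summary.

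The SAP has the tool at hand. Section 4.1.2 states: "Change from baseline is defined as the post baseline value minus the baseline value". Neighbouring sections use it; for pachymetry (7.1.9), "The actual value and change from baseline in corneal thickness will be calculated for each post-baseline visit". Sections 7.1.8 (cup-to-disc ratio) and 7.1.10 (endothelial cell density) go further and plan categories of change by visit and at the worst post-baseline value.

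SAP section 1 gives the SAP precedence over the protocol on statistical definitions and methods. The visible text gives no reason for leaving change out of 7.1.11.

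**The concern.** The protocol's Introduction names ocular hyperemia as a side effect of prostaglandin analogues, the class that both implants deliver. A reader comparing two elution rates with timolol will want to know how many study eyes became redder after treatment.

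A count of grades at a visit does not answer that. A subject with the same grade before and after treatment is counted exactly like one who newly reached it, and improvement in some subjects cancels worsening in others. Baseline redness is plausible here: subjects may enter untreated or on one to three medications that are then washed out. Because the SAP's methods prevail, following 7.1.11 as it reads would leave the protocol's listed outcome without a summary.

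**Working it through.** The documents state no hyperemia rate or related figure, so there is nothing to reproduce. The check asks what the planned table can and cannot determine.

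**Inputs.** Approximately 150 subjects randomized 1:1:1 (Protocol 4.1), so n = 150/3 = 50 per arm. All hyperemia counts and rates below are assumptions for illustration.

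**1. Number newly worsened, from visit counts alone.** Let b subjects in an arm be at or above a given grade at baseline and m at a visit. Let w be the number who moved from below that grade to at or above it. Of the m subjects, m − w were already there at baseline, and that number lies between 0 and b. The w subjects must also come from the n − b who started below. Hence

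max(0, m − b) ≤ w ≤ min(m, n − b).

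| b (baseline) | m (visit) | minimum w | maximum w |
|---|---|---|---|
| 5/50 | 20/50 | max(0, 15) = 15 | min(20, 45) = 20 |
| 15/50 | 20/50 | max(0, 5) = 5 | min(20, 35) = 20 |
| 20/50 | 20/50 | max(0, 0) = 0 | min(20, 30) = 20 |

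In the middle row the answer lies anywhere from 5/50 = 10% to 20/50 = 40% of the arm. The range is narrow when few eyes are red at baseline and wide when many are. Counts in the other grades do not tighten it, because they too say nothing about which subjects moved.

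**2. Offsetting movement.** If 10 subjects cross the grade upward and 8 others downward, the count rises by 10 − 8 = 2 subjects (2/50 = 4 points), although 10/50 = 20% of the arm worsened.

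**3. Does the comparison between arms suffer?** Suppose a share p of each arm has baseline redness that persists, and new onset among the rest is 30% on implant and 10% on control. With p = 0.30:

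- Visit prevalence: 0.30 + 0.70 × 0.30 = 51% and 0.30 + 0.70 × 0.10 = 37%, a difference of 14 points.
- Newly red as a share of the arm: 0.70 × 0.30 = 21% and 0.70 × 0.10 = 7%, also a difference of 14 points.

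The difference between arms is the same. What the visit table cannot give is the level within each arm: it shows 51% where 21% are new.

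**4. Chance imbalance at baseline.** If 20% to 40% of eyes have some baseline redness, the 95% chance range for the baseline difference between two arms is ±1.96 × √(2p(1 − p)/50). That is ±1.96 × 0.080 = ±15.7 points at p = 0.2 and ±1.96 × 0.098 = ±19.2 points at p = 0.4. This describes baseline only; it reaches follow-up in full only if the redness persists completely.

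**The case against.** Several points on the other side are sound.

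- **The plan was conditional.** Protocol 5.2 and the Summary make the change analysis subject to feasibility, and 9.6.5 asks only for descriptive statistics by visit and arm, which 7.1.11 supplies. This stands as a limit: the SAP narrows a partly conditional plan. However, 9.5.2 lists the outcome without the condition, and a baseline grade is collected, so nothing visible suggests that the analysis is infeasible.
- **The comparison is randomized.** A reader might infer that baseline redness biases implant against timolol. The documents do not support that. Randomization balances it in expectation, and step 3 shows the difference between arms preserved. Baseline is also an assessment time, so the table may show each arm's starting distribution, where a chance imbalance would be visible.
- **Worsening is recorded elsewhere.** There is a subject listing. Protocol section 10 makes a significant change from baseline an adverse event, and SAP 7.1.2 tabulates ocular events. These help, but a listing is not a summary, and smaller grade changes may never be reported as events.
- **Part of 7.1.11 is not visible.** The gap follows the statement of how hyperemia is scored and precedes the analysis sentence, so it most likely holds the grading scale. Table shells are in a separate document. One can say only that the visible text names no change summary, not that none will be produced.
- **A change count is imperfect.** It includes grading noise and has floor and ceiling limits. If redness from a washed-out drop fades, it can mask new redness of equal grade. A shift table therefore does not isolate treatment-related redness, but it shows movement that grade counts cannot.

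**Conclusion.** The point holds as a gap in a descriptive safety summary. The protocol lists change from baseline in hyperemia as an outcome, and the governing SAP section, as far as it can be read, plans only grade counts by arm and visit plus a listing. Those counts leave the number who worsened undetermined: 5 to 20 of 50 under the assumed 15/50 and 20/50, narrower or wider with other baseline counts. The size rests on about 50 per arm and on illustrative counts, since the documents give no hyperemia rates.

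Two stronger readings should be resisted. The planned table is not a biased comparison of the arms. Nor do the documents give grounds for treating the reading-center grade as the main one; 7.1.11 already reports both sources. With no formal safety testing and hyperemia one of many safety measures, this is a cheap improvement.

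**What to change.** Keep the grade-by-visit table in SAP 7.1.11 and add, by treatment group for the study eye:

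1. a shift table of baseline grade against grade at each post-baseline visit;
2. the number and percentage of subjects with an increase of at least one grade from baseline, by visit and as the worst post-baseline change, following the pattern of 7.1.8 and 7.1.10.

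Produce both for the CRF grades and for the reading-center grades. If change from baseline has been judged not feasible, say so in 7.1.11 and give the reason.

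The cost is one or two further descriptive tables from data already collected. Subjects without a baseline grade drop out of the new tables only, so their number should be shown. A footnote should say that raw worsening counts include some grading variation and are limited at the ends of the scale, so they are best read across arms and beside the grade-by-visit table.
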